## How much of a problem is this for you?

Not at all

Sometimes

A lot

ID#	_____
Date:	_____

# PedsQL™

## Pediatric Quality of Life Inventory

Version 4.0

### CHILD REPORT (ages 8-12)

#### DIRECTIONS

On the following page is a list of things that might be a problem for you. Please tell us **how much of a problem** each one has been for you during the **past ONE month** by circling:

- 0 if it is **never** a problem
- 1 if it is **almost never** a problem
- 2 if it is **sometimes** a problem
- 3 if it is **often** a problem
- 4 if it is **almost always** a problem

There are no right or wrong answers.  
If you do not understand a question, please ask for help.

PedsQL 

*In the past **ONE month**, how much of a **problem** has this been for you ...*

ABOUT MY HEALTH AND ACTIVITIES (problems with...)	Never	Almost Never	Some- times	Often	Almost Always
1. It is hard for me to walk more than one block	0	1	2	3	4
2. It is hard for me to run	0	1	2	3	4
3. It is hard for me to do sports activity or exercise	0	1	2	3	4
4. It is hard for me to lift something heavy	0	1	2	3	4
5. It is hard for me to take a bath or shower by myself	0	1	2	3	4
6. It is hard for me to do chores around the house	0	1	2	3	4
7. I hurt or ache	0	1	2	3	4
8. I have low energy	0	1	2	3	4

ABOUT MY FEELINGS (problems with...)	Never	Almost Never	Some- times	Often	Almost Always
1. I feel afraid or scared	0	1	2	3	4
2. I feel sad or blue	0	1	2	3	4
3. I feel angry	0	1	2	3	4
4. I have trouble sleeping	0	1	2	3	4
5. I worry about what will happen to me	0	1	2	3	4

HOW I GET ALONG WITH OTHERS (problems with...)	Never	Almost Never	Some- times	Often	Almost Always
1. I have trouble getting along with other kids	0	1	2	3	4
2. Other kids do not want to be my friend	0	1	2	3	4
3. Other kids tease me	0	1	2	3	4
4. I cannot do things that other kids my age can do	0	1	2	3	4
5. It is hard to keep up when I play with other kids	0	1	2	3	4

ABOUT SCHOOL (problems with...)	Never	Almost Never	Some- times	Often	Almost Always
1. It is hard to pay attention in class	0	1	2	3	4
2. I forget things	0	1	2	3	4
3. I have trouble keeping up with my schoolwork	0	1	2	3	4
4. I miss school because of not feeling well	0	1	2	3	4
5. I miss school to go to the doctor or hospital	0	1	2	3	4

ID#	_____
Date:	_____

# PedsQL™

## Pediatric Quality of Life Inventory

Version 4.0

### TEEN REPORT (ages 13-18)

**DIRECTIONS**

On the following page is a list of things that might be a problem for you. Please tell us **how much of a problem** each one has been for you during the **past ONE month** by circling:

- 0 if it is **never** a problem
- 1 if it is **almost never** a problem
- 2 if it is **sometimes** a problem
- 3 if it is **often** a problem
- 4 if it is **almost always** a problem

There are **no right or wrong** answers.  
If you do not understand a question, please ask for help.

PedsQL 2

In the past **ONE month**, how much of a **problem** has this been for you ...

ABOUT MY HEALTH AND ACTIVITIES (problems with...)	Never	Almost Never	Some- times	Often	Almost Always
1. It is hard for me to walk more than one block	0	1	2	3	4
2. It is hard for me to run	0	1	2	3	4
3. It is hard for me to do sports activity or exercise	0	1	2	3	4
4. It is hard for me to lift something heavy	0	1	2	3	4
5. It is hard for me to take a bath or shower by myself	0	1	2	3	4
6. It is hard for me to do chores around the house	0	1	2	3	4
7. I hurt or ache	0	1	2	3	4
8. I have low energy	0	1	2	3	4

ABOUT MY FEELINGS (problems with...)	Never	Almost Never	Some- times	Often	Almost Always
1. I feel afraid or scared	0	1	2	3	4
2. I feel sad or blue	0	1	2	3	4
3. I feel angry	0	1	2	3	4
4. I have trouble sleeping	0	1	2	3	4
5. I worry about what will happen to me	0	1	2	3	4

HOW I GET ALONG WITH OTHERS (problems with...)	Never	Almost Never	Some- times	Often	Almost Always
1. I have trouble getting along with other teens	0	1	2	3	4
2. Other teens do not want to be my friend	0	1	2	3	4
3. Other teens tease me	0	1	2	3	4
4. I cannot do things that other teens my age can do	0	1	2	3	4
5. It is hard to keep up with my peers	0	1	2	3	4

ABOUT SCHOOL (problems with...)	Never	Almost Never	Some- times	Often	Almost Always
1. It is hard to pay attention in class	0	1	2	3	4
2. I forget things	0	1	2	3	4
3. I have trouble keeping up with my schoolwork	0	1	2	3	4
4. I miss school because of not feeling well	0	1	2	3	4
5. I miss school to go to the doctor or hospital	0	1	2	3	4

WHO-DDE	World Health Organization Drug Dictionary Enhanced

1. Introduction

This international, multicenter, single-arm, open-label study is designed to evaluate the safety, tolerability and pharmacokinetics of a body-weight adjusted riociguat regimen in children from ≥ 6 years to < 18 years of age who have been diagnosed with idiopathic pulmonary arterial hypertension (IPAH), hereditary PAH, or PAH associated with connective tissue disease or congenital heart disease with shunt closure. The study consists of two periods: the *main study treatment period (24 weeks)* and an optional *Long-term extension (LTE) phase*.

Two analyses are planned for this study:

- (1) at the end of the main study treatment period (24 weeks treatment) including the data from the main study treatment period, the safety follow-up as far as available, and the LTE phase for subjects who already entered the LTE phase.
- (2) at the end of the LTE phase: including the data from both periods, i.e. the main study treatment period and the LTE phase.

This statistical analysis plan (SAP) describes the statistical methods and data presentations of analysis (1), i.e. main study treatment period.

The SAP is based on

- Statistical Analysis Plan version 3.0 , dated 24 AUG 2016
- Integrated clinical study protocol version 5.0 [1], including
 - Global Amendment 12, dated 23 AUG 2019
 - Local Amendment 11 (Romania), dated 05 APR 2019
 - Local Amendment 10 (Taiwan), dated 29 MAY 2018
 - Global Amendment 9, dated 13 MAR 2018
 - Local Amendment 8 (Germany), dated 03 NOV 2017
 - Local Amendment 7 (Japan), dated 07 MAR 2017
 - Global Amendment 6, dated 09 JAN 2017
 - Global Amendment 5, dated 31 MAY 2016
 - Local Amendment 4 (Japan), dated 16 MAR 2016
 - Global Amendment 3, dated 24 NOV 2015
 - Local Amendment 2 (Poland), dated 03 NOV 2015
 - Local Amendment 1 (UK), dated 25 AUG 2015
 - Clinical study protocol version 1.0, dated 13 MAR 2015

Planned LTE analysis and also a country-specific analysis for Japan will be covered by separate SAPs.

2. Study Objectives

A descriptive analysis of the safety and efficacy parameters will be performed.

The primary objectives: To evaluate safety, tolerability and pharmacokinetics of oral riociguat treatment.

Secondary objectives: Exploratory efficacy, i.e. to characterize the pharmacodynamic profile of riociguat comprising the following exploratory parameters:

- exercise capacity (6-minutes-walking-distance (6MWD) test),
- functional capacity (measured by WHO Functional class (FC)),
- laboratory biomarkers (N-terminal pro-brain natriuretic peptide (NT-proBNP), or brain natriuretic peptide (BNP)),
- Quality of life (QoL) measurements (Health Survey for Children (SF-10), child health questionnaire and Pediatric Quality of Life Inventory (PedsQL), Generic Core Scales self report),
- echocardiographic parameters,
- time to clinical worsening (TTCW).

Other objectives:

- to assess taste and texture of the pediatric formulation(s) by use of a questionnaire,
- to assess change in right heart catheterization (RHC) parameters (if available) obtained from RHC performed before study enrollment and during study conduct.

3. Study Design

3.1 Design overview

This is an international, multicenter, single-arm, open-label study to evaluate the safety, tolerability and pharmacokinetics of a body-weight adjusted riociguat regimen in subjects aged between ≥ 6 years old and < 18 years old who have been diagnosed with IPAH, hereditary PAH, or PAH associated with connective tissue disease or congenital heart disease with shunt closure. These subjects must be on stable treatment with PAH medications (Endothelin Receptor Antagonists (ERA) and/or Prostacyclin Analogues (PCA)) prior to receiving the first dose of riociguat [2] [3].

At least 20 children on treatment with bosentan or other ERAs are planned to be enrolled in the study, making every effort to enroll equal number of subjects in each of the ≥ 12 to < 18 year and the ≥ 6 to < 12 year age cohort with a minimum of 5 subjects in each age cohort. In case of inadequate availability of subjects in the age group ≥ 6 to < 12 years total enrolment is planned to be stopped only if at least 5 subjects of this younger age group have been enrolled. Enrollment starts with subjects from 12 to < 18 years of age.

The main study comprises 3 periods: pre-treatment phase (Day -14 to Day -1), main study treatment period (24 weeks) and safety follow-up phase (60 ± 8 days). The main study treatment period is divided into the individual titration phase (8 weeks) and maintenance phase (16 weeks). Subjects completing the optional LTE will also perform the safety follow-up visit after 60 ± 8 days after LTE.

After providing written informed consent and assent (if applicable), subjects undergo a screening evaluation to determine their eligibility. Eligible subjects – once on stable background treatment with ERA and/or PCA- start body-weight adjusted individual dose titration (IDT) regimen. After the individual titration phase of maximum of 8 weeks, subjects enter the 16-week maintenance phase. The last dose administered at Visit 4 (see Figure 3–1 below) is determined as individual optimal dose and subject receives that treatment during the maintenance phase.

Subjects of the older age cohort (≥ 12 to < 18 years) are treated first. After 5 subjects of this age cohort have reached their optimal dose and received this dose until assessment of their first control X-ray of left hand at week 24, an independent Data Monitoring Committee (DMC) provides recommendations to the Steering Committee (SC) whether to continue with enrolment in this age cohort and open enrolment in the subsequent lower age cohort (≥ 6 to < 12 years). Only after obtaining positive safety and efficacy data in the first 5 patients, enrolment in the group from 6 to less than 12 years of age will be started.

Children who require treatment with riociguat for more than 24 weeks will be offered participation in an extension study and continuation until market approval of riociguat for the pediatric population unless local requirements prevent it, or until they are ≥ 18 years of age (whatever comes first). Subjects reaching adulthood can be transitioned to commercially-available Adempas.

3.2 Dosing overview

The individual optimal study dose will be defined during the titration phase of 8 weeks. The last dose administered during the titration phase will be administered during a 16-week maintenance phase. Subjects of the older age cohort (≥ 12 to < 18 years) are treated first. After 5 subjects of this age cohort were treated for 24 weeks, an independent DMC will provide recommendations to the further conduct of the study.

Riociguat is administered to all subjects using an individual dose titration scheme according to a body weight-adjusted dose to achieve a similar exposure as that observed in adults treated for PAH. The individual optimal (maintenance) dose is to be determined based on patient's monitoring of systolic blood pressure, well-being and clinical status. For children with < 50 kg body weight at screening, a body weight adjusted dosing will be applied. Children with ≥ 50 kg body weight at screening will receive adult doses.

[figure not shown]
In subjects with a body-weight below 50 kg at screening, riociguat is administered as oral suspension TID with or without food. Subjects with a body-weight ≥ 50 kg at screening receive riociguat as tablet formulation.

The following tablet strengths are available: 0.5 mg, 1.0 mg, 1.5 mg, 2.0 mg, and 2.5 mg. An oral suspension formulation of 0.15 mg/mL is also available.

Subjects with < 50 kg body weight at screening start with body-weight adjusted riociguat dose equivalent to the exposure of 1.0 mg TID in adults. Subjects with ≥ 50 kg body weight at screening start with dose 1.0 mg TID. During the individual titration period, the dose is up-titrated every 2 weeks (± 2 days) at the discretion of the investigator, based on subject's peripheral systolic blood pressure (SBP) and general tolerability measured at trough before intake of the next higher dose of riociguat. The maximum dose is the dose equivalent to the exposure of 2.5 mg in adults TID. Dose reductions for safety reasons are allowed at any time. The individual dose titration period does not exceed 8 weeks.

Dosing steps and dose equivalents in adults are shown in Figure 3–1 :

Figure 3–1: Dosing Schedule

TID = three times a day; V = Visit

At each titration visit, the individual dose is assigned based on the following algorithm where peripheral SBP will be measured (by oscillometry with the same calibrated oscillometry unit in each center) at trough before intake of the first dose of the day.

Dose titration algorithm

- If SBP is less than 5 mmHg lower than the age-, sex- and height-adapted level of the 50th SBP percentile [4], increase riociguat dose (+0.5 mg dose-equivalent TID)
- If SBP is ≥ 5 mmHg but less than 10 mmHg lower than the age-, sex- and height-adapted level of the 50th blood pressure (BP) percentile, maintain dose of riociguat.
- If SBP is ≥ 10 mmHg lower than the age-, sex- and height-adapted level of the 50th BP percentile, reduce riociguat dose (- 0.5 mg dose-equivalent TID).
- If any SBP is ≥ 5 mmHg lower than the age-, sex- and height-adapted level of the 50th BP percentile, with clinical symptoms of hypotension such as dizziness or presyncope, stop study treatment; restart after 24 hours with reduced dose (- 0.5 mg dose-equivalent TID).

Down-titration of riociguat is possible for safety reasons at any time point. If at any time, the subject has symptoms of hypotension, temporarily stop the medication and restart after 24 hours with a reduced dose (decrease dosage by 0.5 mg dose-equivalent TID).

At the end of the individual titration phase (Visit 4), the subjects should have reached their individually adjusted dose (maximum equivalent dose of 2.5 mg riociguat TID). The established individual equivalent dose is then taken as optimal dose to be administered during the 16-week maintenance phase. Dose reductions for safety reasons are allowed in the maintenance phase, but a subsequent re-increase is not possible. During the LTE phase the dose may be up-titrated at the investigator’s discretion.

Subjects not tolerating the body-weight adjusted riociguat 0.5 mg TID are to withdraw from study.

During the LTE, subjects receiving stable equivalent dose of 1.0 mg, 1.5 mg, 2.0 mg, or 2.5 mg TID as oral suspension can switch to the tablet formulation at the discretion of the investigator.

4. General Statistical Considerations

4.1 General Principles

The statistical evaluation will be performed by using the software package Statistical Analysis Software (SAS) release 9.4 or higher (SAS Institute Inc., Cary, NC, USA). All variables will be analyzed by descriptive statistical methods.

1. The number of data available and missing data, mean, standard deviation (SD), minimum, 25% and 75% quartiles, median, and maximum will be calculated for metric data. Mean, median, quartiles and SD will be reported to one decimal place greater than the data were collected. Minimum and maximum values will be reported with the same precision as they were collected. The same metrics will be calculated for the change in parameters between Baseline and visits after Baseline.
2. Frequency tables will be generated for categorical data. These include the counts and percentages of each category including the category 'missing' as a separate category, if applicable. Percentages will be calculated using a denominator of all subjects in the specified population, and the percentage values will be reported to one decimal place. If an incidence is $< 0.1\%$ but $> 0\%$, it will be displayed as " $<0.1\%$ ".
3. If no data exists for a table, an empty table will be provided. The text in that table should read "No data matched the selected criteria".
4. For tables that fit horizontally on a single page, and that are more than one page in length, "Continued" will be added to the bottom of all but the last page. The word "Continued" must be added to the title for all pages after the first page and to the bottom of the page for all pages from the first to the second to last page.
5. For event-based tables the number of subjects should be displayed next to the treatment with the syntax "(N=x)". For tables where the N is the number of subjects and also used as the denominator "N=x (100%)" is to be used.
6. In frequency tables, if "n=0", then only "0" should be displayed; "(0.0%)" will not be displayed.
7. When numerator and denominator values are "0", do not use brackets. Use the following: "0/0", not "0/0 (%)".
8. All listings will be presented for subjects with their subject identifier, age at screening, sex and race.

The structure of analyses datasets and layout of analysis data displays will follow Bayer standards in the following order of priority: Riociguat Global Standards, Global Medical Standards, and Global Standards for Data Display. Study-specific specifications may be added if required and not covered by the Global Standards.

4.2 Handling of Dropouts

A subject who discontinues study participation prematurely for any reason, as specified in the protocol in section 8.9, is defined as a “dropout” if the subject has already started treatment. Dropouts will not be replaced.

In all subjects who prematurely discontinue study drug at any time after Visit 1 and before Visit 9 for reasons other than withdrawal of informed consent, an end-of-treatment visit has to be performed. The same procedures as at Visit 9 will be performed with the exception of the X-ray of left hand.

For all subjects stopping study medication either at the end of treatment or prematurely discontinuing the study at any time, a safety follow-up visit 60 days (± 8 days) after last study medication intake should be performed.

If the subject or parent(s)/legal representative(s) withdraw(s) consent to treatment with study drug, the investigator asks to continue with study visits as planned, only with the aim to collect potential study outcomes and AEs. If the subject/parent(s)/legal representative(s) state to the investigator that they no longer authorize to continue to obtain outcome data, this is respected and documented in the source records, and no further study data are collected.

In all subjects who prematurely discontinue study drug for other reasons than withdrawal of informed consent, study visits takes place as planned to collect potential study outcomes and AEs. The analysis will be performed independently of the fact whether a patient had drug intake or not.

A subject who discontinues the study prior to the first intake of the study treatment is defined as ‘screening failure’.

The number of screening failures and dropouts as well as the respective reasons will be summarized.

The frequency of enrolled subjects not completing screening, treatment phase, safety follow-up for those not entering the long-term extension and associated reasons will be summarized.

A Kaplan-Meier plot of the time from start of study treatment to end of study treatment will be provided. Subjects continuing study treatment in the LTE phase will be censored on his/her end of main phase.

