### **6.1.3 End-of-treatment visit - amended**

For all subjects dropping-off the protocol at any time after V1 and before V9, an end-of-treatment visit has to be performed.

The same procedures as at Visit 9 will be performed with the exception of the x-ray of left hand.

In case RHC is conducted based on medical reasons during the study, record RHC parameters to eCRF.

*(Note: The Section was modified according to Amendment 3, see Section 17.1.1.16. The Section was modified according to Amendment 5, see Section 17.2.1.2. This section was modified according to Amendment 9, see Section 17.4.1.13.)*

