## 8.9 Premature discontinuation of study medication

Subjects must be withdrawn from the study for the following reasons:

- At their own request or at the request of their legally acceptable representative at any time during the study and without giving reasons, a subject may decline to participate further. The subject will not suffer any disadvantage as a result

- If, in the investigator's opinion, continuation of the study would be harmful to the subject's well-being.
- If any AE occurred which is not acceptable in the opinion of the investigator and / or participating parent(s)/legal representative(s) or subject
- Occurrence of adverse drug reactions, which have from the investigator's point of view, a negative impact on the subject's individual risk-benefit ratio.
- If treatment is interrupted for more than 3 days during any individual dose titration phase
- If treatment is interrupted for more than 14 consecutive days during the maintenance phase.
- In case a female subject of childbearing potential is not compliant with pregnancy testing
- In case of lung transplantation
- In case of pregnancy or breast feeding
- In case that the subject fulfills one of the stopping criteria specified in Section 5.1.1
- Subject does not tolerate the lowest possible riociguat dose (0.5 mg TID)
- Patient with pulmonary hypertension associated with idiopathic interstitial pneumonias (PH-IIP)

Discontinuation of bosentan or other ERA treatment (i.e. due to elevated liver enzymes) during the course of the study does not mandate withdrawal of the subject from the study. Also, discontinuation PCA treatment, during the course of the study, does not mandate withdrawal of the subject from the study. The final decision of withdrawal will be the responsibility of the investigator.

The DMC may recommend stopping the trial due to an unfavorable risk benefit assessment during the course of the trial. The final decision to terminate will be the responsibility of the Sponsor.

If the subject or parent(s)/legal representative(s) withdraw(s) consent to treatment with study drug, the investigator will ask to continue with study visits as planned, only with the aim to collect potential study outcomes and AEs. If the subject/parent(s)/legal representative(s) state to the investigator that they no longer authorize to continue to obtain outcome data, this will be respected and documented in the source records, and no further study data will be collected.

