In all subjects who prematurely discontinue study drug for other reasons than withdrawal of informed consent, study visits will take place as planned to collect potential study outcomes and AEs.

*(Note the section was modified according to Amendment 6, see Sections 17.3.1.1 and 17.3.1.2.)*

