4.3 Handling of Missing Data

All missing or partial data will be presented in the subject data listing as they are recorded on the electronic case report form (eCRF). Missing data proportions will be reported.

In general they will not be substituted or replaced, except for the parameters described below.

General rules

- **Efficacy variables**

Last visit is defined as last observed value post-baseline (including unscheduled visits, but not including follow-up), if not specified otherwise.

- **6 Minute Walking Distance**

If a subject dies before Week 24 or during follow-up after termination before Week 24, the worst value = 0 is used.

- WHO Functional Class

If a subject dies before Week 24 or during follow-up after termination before Week 24, the worst value = IV (4) is used.

- **Safety variables**

Last visit is defined as last observed value post-baseline (including unscheduled visits, but not including follow-up), if not specified otherwise.

Treatment emergent events, phases, period and relative days will be derived according to standard guidelines.

A complete date is not needed for the statistical tables, but an imputation on the phase of the study for adverse events and concomitant medications (pre, during or post) is required. The 'minimum' rule will be used for start dates which is first day of month or 1st of January. The 'maximum' rule will be used for end dates which is last day of month or 31st of December.

- **Child Health Questionnaire (SF-10)**

Scores will be provided by QualityMetric Score was generated by QualityMetric.

- **Pediatric Quality of Life Inventory™ (PedsQL™)**

In the case of missing single questionnaire items, the missing data rules in the scaling and scoring document will be followed. Specifically, if more than 50% of the items in the scale are missing, the Scale Scores should not be computed. If 50% or more items are completed: Impute the mean of the completed items in a scale.

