4.5 Data Rules

Unless otherwise specified, baseline is the last available non-missing value prior and up to the time of the first intake of study medication, i.e. first dose of riociguat. Change from baseline is calculated as the value at the post-baseline time point minus the baseline value, i.e. value at time point – value at baseline.

Post-treatment values will be considered treatment-emergent if they start within 2 calendar days after the last day of study drug administration, i.e. the treatment-emergent window will be 2 days.

All data from the electronic case report form (eCRF) will be organized and analyzed according to the scheduled visits. Any additional or unscheduled measurements will be included in the listings according to the date/time of assessment. In the case of multiple observations at a specific visit, the observation that is closest to the target visit will be used in the analyses. If observations have the same distance (before and after) to the target visit, the latest one will be used. If the repeated measurements are all taken on the same day, then the last measurement will be used.

Subgroup analyses will be performed by age cohort (≥ 6 to < 12 years and ≥ 12 to < 18 years) and by concomitant PAH medication (ERA only, ERA + PCA, PCA only) specified at Screening. The patients are assigned to the concomitant PAH medication groups specified before date of treatment according to Standardised Drug Grouping (SDG)/Bayer Drug Groupings (BDG), section 6.1.6. Patient’s assignment to PAH medication grouping is depicted in Table 4–1:

Table 4–1: Concomitant PAH medication grouping

Group	SDG (BDG)	
	Endothelin receptor antagonists	Prostacyclins (including analogues and receptor agonists)
ERA only	Yes	No
ERA + PCA	Yes	Yes
PCA only	No	Yes

Listings will be sorted by subject identifier, visit (if applicable), date and time.

Dates will be formatted as DDMMYYYY. Partial dates will be presented on data listings with dashes for the missing parts, e.g. like --MMYYYY. Listing should only present the collected dates, not imputed dates.

Rounding for all variables will occur only as the last step, immediately prior to presentation in listings and tables. No intermediate rounding will be performed on derived variables. The standard rounding practice of rounding numbers ending in 0-4 down and numbers ending 5-9 up will be employed.

Every table, listing and figure will be produced with an electronic date stamp to document when it was produced.

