6.4 Safety

The primary objective of this study is to evaluate safety and tolerability of riociguat in children with PAH. Primary endpoint of the study is: Change from baseline to end of treatment (week 24) of safety and tolerability.

Beside the number of subjects who discontinued prematurely, safety and tolerability will be assessed by incidence of adverse events and serious adverse events, recording of ECGs, vital signs, body weight, left hand X-ray and laboratory panel.

Safety data will be presented in data listings, and summarized in tables for subjects in the SAF.

AEs will be coded according to the MedDRA, last available version, and analyzed by SOC and PT.

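### The week-24 safety changes in blood pressure, heart rate and laboratory values can include off-drug readings, and the SAP plans no on-treatment counterpart

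*SAP*

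**What the plan says.** Protocol 8.9 provides for visits after stopping: "In all subjects who prematurely discontinue study drug for other reasons than withdrawal of informed consent, study visits will take place as planned". SAP 4.2 repeats this and continues: "The analysis will be performed independently of the fact whether a patient had drug intake or not".

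SAP 6.4 sets the target: "Primary endpoint of the study is: Change from baseline to end of treatment (week 24) of safety and tolerability". Protocol 6.2 equates end of treatment with Visit 9 at week 24. It lists heart rate, blood pressure, bone age and laboratory parameters as the primary changes and puts ECG among the other safety outcomes. SAP 6.4 instead lists ECG and body weight directly under the primary endpoint.

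For safety variables, SAP 4.3 says: "Last visit is defined as last observed value post-baseline (including unscheduled visits, but not including follow-up), if not specified otherwise". SAP 4.5 says of values after the last dose that "the treatment-emergent window will be 2 days". The changes from baseline planned in SAP 6.4.2 (laboratory), 6.4.4 (vital signs) and 6.4.5 (ECG) refer neither to that window nor to drug intake.

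**The concern.** The label and the data rule describe different quantities. A change to end of treatment suggests the state of a child on riociguat. An analysis that ignores drug intake describes the state at week 24 of everyone who started. For a child who stopped at week 3, Visit 9 falls 21 weeks after treatment ended (24 − 3).

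Blood pressure is where this matters most. Dose titration is driven by systolic pressure, and symptomatic hypotension is an event of special interest (Protocol 5.1.1 and 8.8). Some of those who stop may therefore do so because of the variable being summarised. If pressure recovers off drug, the recovered reading stands in the riociguat column at week 24, and no table shows how many children in that column are off drug. The numbers are small, and these outputs also go to the DMC.

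**Working it through.** **What the SAP applies to each output**

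| Output | On-drug limit stated in the SAP |
|---|---|
| Adverse events (6.4.1) | Yes, up to 2 days after treatment ends |
| Specific laboratory abnormalities (6.4.2) | Yes, called treatment-emergent |
| Laboratory change from baseline (6.4.2) | None |
| Vital-sign change from baseline (6.4.4) | None |
| ECG change from baseline (6.4.5) | None |
| Last visit, safety variables (4.3) | None; only follow-up is excluded |

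Protocol 7.4.1 also asks for treatment-emergent out-of-range laboratory values and treatment-emergent ECG abnormalities. SAP 6.4.2 uses the term only for its specific-abnormalities table, and SAP 6.4.5 does not use it.

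**Inputs for the size.** The plan has no figure to reproduce. The study is descriptive, and its number, at least 20 children on an ERA, rests on feasibility (Protocol 7.5). The minimum age cohort is 5 (Protocol 4.1). Neither document gives a stopping rate or an off-drug effect, so both are assumed below.

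**Formula.** Let f be the share of children off drug at week 24, and r the off-drug change as a fraction of the on-drug change, with the same on-drug effect in every child. Then

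reported mean = on-drug mean × [1 − f(1 − r)].

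| Off drug | f | Shrinkage, r = 0 (full reversal) | Shrinkage, r = 0.5 | Reported mean if the on-drug SBP change is −5 mmHg (assumed), r = 0 |
|---|---|---|---|---|
| 1 of 20 | 0.05 | 5% | 2.5% | −4.75 |
| 2 of 20 | 0.10 | 10% | 5% | −4.50 |
| 3 of 20 | 0.15 | 15% | 7.5% | −4.25 |
| 5 of 20 | 0.25 | 25% | 12.5% | −3.75 |
| 1 of 5 | 0.20 | 20% | 10% | −4.00 |

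The 1-of-5 row applies to vital signs and ECG, which are presented by age group. Laboratory data are presented for all ages together.

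**Direction.** With r = 1 there is no shrinkage. With r = 1.5, for example after another blood-pressure-lowering PAH drug is started, f = 0.10 gives 1 − 0.10 × (1 − 1.5) = 1.05, so the change is inflated by 5%.

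**How likely it is to arise.** For an assumed off-drug rate d at week 24, the chance of at least one off-drug child among n is 1 − (1 − d)^n. For d = 5%, 10% and 20% this is 64%, 88% and 99% among 20 children, and 23%, 41% and 67% among 5.

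**The case against.** Five points can be made for the plan.

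- Analysing all data regardless of intake is a legitimate choice, and using the week-24 value follows the protocol's own definition of end of treatment. This stands, provided the table is labelled for what it is. It still leaves no on-drug reading of the same change.
- A child who stops for hypotension is not hidden. Adverse events use the two-day window, hypotension is an event of special interest, events leading to discontinuation are tabulated and listed, reasons for down-titration are summarised, and time on treatment has a Kaplan-Meier plot. Readings before stopping stay in their own visit columns. This stands, and it limits the point to the change-from-baseline summaries.
- Restricting the by-visit tables to on-drug values would leave only children still on treatment, which is a selection of its own. This also stands, so the all-data tables should not be replaced.
- It is unclear how many off-drug values will exist. Protocol 8.9 heads its list "Subjects must be withdrawn from the study for the following reasons" yet keeps visits going. Protocol 6.1 assigns a follow-up period to those who stop prematurely, and 6.1.3 says: "For all subjects dropping-off the protocol at any time after V1 and before V9, an end-of-treatment visit has to be performed". If visits after stopping count as follow-up, SAP 4.3 keeps them out of the last-visit value. That is a reason to define the mapping.
- Derivations may be fixed in sponsor standards or table shells, which the two documents cite but do not contain. That is possible, but the SAP text does not say so.

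A reader might go further and infer that the strongest responders are replaced by recovered values and the mean is understated by 22% to 45%. Such figures need assumed SBP changes of −15 mmHg in stoppers on drug, −6 in the others and 0 off drug. With 3 stoppers of 20, the all-data week-24 mean is (3 × 0 + 17 × −6)/20 = −5.10, and the mean of last on-drug values is (3 × −15 + 17 × −6)/20 = −7.35, so 1 − 5.10/7.35 = 31%. With 2 and 5 stoppers the same sum gives 22% (−5.4 against −6.9) and 45% (−4.5 against −8.25). That comparator mixes early and week-24 readings. Against week-24 values of children still on drug (−6.0), the gaps are 10%, 15% and 25% for 2, 3 and 5 stoppers. The documents support none of these inputs.

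**Conclusion.** The point holds as a gap in definition. As written, the SAP lets off-drug blood pressure, heart rate and laboratory values enter the safety change labelled to end of treatment, and it offers no on-treatment version. ECG is affected in the same way, but whether it is primary depends on which document is read.

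Under full reversal and a uniform effect, the week-24 mean loses 5% to 25% for 1 to 5 of 20 children off drug, and 20% for 1 of 5. Partial reversal makes this smaller. The direction is not guaranteed, because treatment started after stopping could offset or reverse it. No hypothesis test is at stake, and the adverse-event component of the primary endpoint is sound. This is an inexpensive improvement to how the primary safety change can be read, and the documents do not show that the safety profile will look better than it is.

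**What to change.** In SAP 4.2, 4.3 and 6.4:

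1. Keep the all-data by-visit tables and label them as including values after stopping.
2. For vital signs, laboratory values, ECG and body weight, add a change from baseline to the last value up to the last dose plus 2 days, the SAP's existing window. Use this as the end-of-treatment summary.
3. Show the number of children off drug at each visit.
4. State how the end-of-treatment visit and any visits after stopping map to week 24, to last visit and to follow-up. The passages in Protocol 6.1, 6.1.3 and 8.9 on what happens after stopping must be reconciled first.
5. Reconcile the status of ECG between Protocol 6.2 and SAP 6.4.

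The cost is SAP wording, one flag in the analysis datasets and one more set of tables; no new data are needed. The on-treatment row will mix readings from different weeks, so the time of the last value should be shown beside it. Some early stoppers will contribute little. After baseline, laboratory tests are scheduled only at Visits 5 and 9 and the end-of-treatment visit, and ECG after Visit 1 only at Visit 9 and the end-of-treatment visit. A child who stops at week 3 and is seen more than 2 days after the last dose would have no scheduled on-drug laboratory value and no on-drug ECG after Visit 1.
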